To determine the effect of live and pre-recorded music therapy on vital variables in newborns older than 32 weeks hospitalized in the Neonatal Intensive Care Unit of the Clinica Universitaria Colombia (CUC).

Secondary objectives

- To describe the demographic and clinical characteristics of study participants.
- To analyze the effect of live and pre-recorded music therapy on the vital signs (heart rate, respiratory rate, and oxygen saturation) of study participants.
- To categorize the stressful events, present in neonatal intensive care units according to their origin, namely auditory, tactile, and visual.

Methodology

Study Design

A prospective analytical, pragmatic clinical trial-type study will be conducted to provide evidence on the benefits of health interventions in real-world settings (in routine clinical practice). The study will be conducted at the Neonatal Intensive Care Unit of the CUC in Bogotá D.C. during the period from May 1st to June 30th, 2024.

Study Population

The study will include newborns who are older than 32 weeks gestational age at birth and who are hospitalized in the Neonatal Intensive Care Unit of the CUC.

Inclusion criteria

All newborns who meet the following inclusion criteria will be included:

- Gestational age at birth greater than or equal to 32 weeks.
- Birth weight greater than or equal to 1500 grams.
- Be at least 72 hours of postnatal age.

Exclusion criteria

All newborns who meet at least one of the following criteria will be excluded:

- Respiratory disturbances in the last 48 hours such as:
 - o Apnea or Brief Resolved Unexplained Events (BRUE).
 - o Need for invasive mechanical ventilation.
- Hemodynamic alterations in the last 48 hours such as:
 - o Hypotension (systolic, diastolic, or mean BP < P5) or hypertension (systolic, diastolic, or mean BP > P95).
 - o Bradycardia (HR < 100/min).
 - o Shock of any etiology
 - o Requirement for volume expanders, infusion of inotropic, vasodilators and/or prostaglandin E1
- Neurological alterations such as:
 - o Perinatal asphyxia at birth manifested by the need for resuscitation, APGAR < 3 at 5 minutes and/or ≤ 5 at 10 minutes, and metabolic acidosis in cord gases with pH < 7 and BE < -12.
 - o Hypoxic-ischemic encephalopathy.
 - o Seizure syndrome for up to 48 hours after the last clinical event or alteration of the brain pattern.
 - o Interventricular hemorrhage in preterm infants in the first week of diagnosis.

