- Management with Extracorporeal membrane oxygenation (ECMO) and/or nitric oxide.
- Temperature less than 36.5 C or greater than 37.5 C.
- Patient under pharmacological sedation or use of beta-blockers.

- Congenital heart disease, operated on or not.
- Congenital malformations.
- Surgical emergencies or recovery from a surgical procedure performed within the last 48 hours.

Sample size

The sample size was determined using the G*Power 3.1.9.7 program, with a confidence level of 95%, statistical power of 90%, mean difference in heart rate between the live music therapy group (140 bpm), prerecorded music therapy group (127 bpm), and the control group (147 bpm). A total sample size of 45 was calculated, with a ratio of 1:1:1 between groups. This equates to 15 participants in each group.

Sample Selection

Stratified random sampling will be used, with two strata according to gestational age defined as follows: stratum 1 neonates <37 weeks and stratum 2 neonates ≥37 weeks. Blocked randomization (block of size 3) will be used for each stratum and for the allocation of participants to each of the intervention and control groups (1:1:1). The allocation sequence will be generated by Microsoft Excel®.

The random assignment will be concealed through the use of opaque envelopes, which will be sealed and numbered sequentially. These envelopes will be carried out by the operational coordinator of the project. The carbon paper inside the envelope will transfer the details of the random number and the group to which it will be assigned (A, B or C). This will ensure that the envelope is not permeable to intense light. The envelopes will be sealed with tamper-evident security tape and will be opened sequentially only after the participant, meeting the eligibility criteria, has received the envelope. The envelopes will be kept in a folder that will be kept on a locked shelf within each unit, which will be in the custody of the project's operational coordinator.

Blinding

It is not possible to blind the participants or the music therapist from randomization due to the nature of the intervention.

Variable Matrix

Variable name	Operational Definition	Nature and Scale of Measurement.	Unit of measurement
Date of birth	Time in which he was born.	Quantitative – Discrete	Day/Month/Year

Sex	Biological characteristics that determine whether it is female or male.	Qualitative – Nominal – Dichotomous	1: Female 2: Male

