Heart rate	Number of heartbeats measured at minute 0, from minute 0 to 30 minutes after the procedure continuously and 30 minutes after the intervention.	Quantitative – Discrete	Beats per minute (bpm)
Respiratory rate	Number of breaths measured at minute 0, from minute 0 to 30 minutes after the intervention continuously and at 30 minutes after the intervention.	Quantitative – Discrete	Breaths Per Minute (rpm)
Oxygen saturation	Measurement of the percentage of oxygen availability in the blood, measured at minute 0, from minute 0 to 30 minutes after the intervention continuously and at 30 minutes after the intervention.	Quantitative – Discrete	Percentage of SaO ₂ (SaO ₂ %)

Description of interventions

Music therapy is a non-pharmacological therapeutic intervention that will be implemented through two modalities: live and pre-recorded music. Group A will be comprised of patients who have been exposed to live music, which will be carried out by a music therapist using the guitar as the only musical instrument. Instrumental lullabies will be used, which will be selected by the patients' legal guardians. Group B corresponds to patients who will be exposed to pre-recorded music, of the genre of lullabies, instrumental type, using a speaker that will be placed inside the patient's incubator. Group C will be those patients in whom no musical intervention will be performed.

The patient will be placed in an incubator, monitored with a vital sign monitor and pulse oximetry, and under the supervision of a research assistant. The research assistant will be responsible for recording the variables at minute 0, from minute 0 to minute 10, and 30 minutes after the completion of music therapy or non-intervention. The volume will be controlled in the three groups by means of a decibel regulator, with a maximum volume of 70 dB.

During the intervention and for a period of 30 minutes following its conclusion, singing will be prohibited by the music therapist or, in the case of groups A and B, by the parents. This prohibition will be implemented in the same manner in group C, which will be devoid of any form of music exposure in order to prevent the introduction of confounding variables. Both live and pre-recorded music will be instrumental in nature, lacking any lyrics. In accordance with the protocol for admission to the neonatal unit, the use of electronic devices is restricted. Consequently, patients will not be exposed to auditory stimuli of this nature.

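### With one fixed block of 3 for three visibly different arms, 14 or 15 of the 45 assignments can be deduced from earlier ones by anyone who knows the block size

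*Protocol*

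**What the plan says.** All of the following is in the protocol; no SAP was available.

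- **Sample Selection** sets two gestational-age strata (below 37 weeks, and 37 weeks or more) and states: "Blocked randomization (block of size 3) will be used for each stratum". It names no other block size, no random variation in size, and no withholding of the size from recruiting staff.
- **Sample size** gives the total and the ratio: "A total sample size of 45 was calculated, with a ratio of 1:1:1 between groups".
- **Sample Selection** also describes concealment: "The random assignment will be concealed through the use of opaque envelopes, which will be sealed and numbered sequentially". The envelopes are lined with carbon paper, taped with tamper-evident tape, locked away by the operational coordinator, and opened in order once eligibility is met.
- **Blinding** states: "It is not possible to blind the participants or the music therapist from randomization due to the nature of the intervention".
- **Description of interventions** sets out a live guitarist in Group A and a speaker in the incubator in Group B. For the control arm: "Group C will be those patients in whom no musical intervention will be performed".
- **Study Design** names one centre: "The study will be conducted at the Neonatal Intensive Care Unit of the CUC".

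**The concern.** Three is the smallest block that can hold three arms at 1:1:1, so it is the most predictable choice available. The envelope procedure is careful, but it only stops someone from reading the next assignment. It cannot stop someone from working that assignment out from what has already happened at the bedside.

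Concealment matters because foreknowledge of the arm can influence which infant is enrolled, or when. The Inclusion criteria section says all newborns who meet the criteria enter, which limits the choice of infant but leaves timing open. Several exclusions change from day to day, such as those headed "Respiratory disturbances in the last 48 hours such as" and the temperature range of 36.5 to 37.5 C, and the 72 hours of postnatal age is only a minimum. Enrolling an infant a little earlier or later, when its state differs, could shift heart rate between arms at entry.

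**Working it through.** **Inputs.** Block size 3, two strata and three arms at 1:1:1 (Sample Selection); N = 45, 15 per arm (Sample size). The split of the 45 between strata is not given, so all splits are considered.

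**The plan's own figure.** The total of 45 is taken as stated. It cannot be fully reproduced because no within-group SD is given. The planned means of 140, 127 and 147 bpm (average 138) have SD √((2² + 11² + 9²)/3) = 8.29 bpm. In a one-way ANOVA at alpha 0.05 and 90% power, N = 45 then follows for a within-group SD of about 14.5 to 15.1 bpm. Nothing below depends on this.

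**Assignments known for certain with block 3.** Each complete block is an ordering of A, B and C, so its third member is forced. With stratum sizes n1 + n2 = 45:

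certain = floor(n1/3) + floor(n2/3)

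- n1 a multiple of 3 (so n2 is too), for example 21/24: 7 + 8 = 15, or 33% of 45.
- Otherwise, for example 22/23: 7 + 7 = 14, or 31% of 45.

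Of the 46 possible splits, 16 give 15 and 30 give 14.

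**Best-guess success with block 3.** Expected correct guesses per complete block are 1/3 + 1/2 + 1 = 11/6.

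- 15 complete blocks: 15 × 11/6 = 27.5; 27.5/45 = 61.1%.
- 14 complete blocks, plus one stratum left one infant into a block and the other two infants in: 14 × 11/6 + 1/3 + (1/3 + 1/2) = 26.83; 26.83/45 = 59.6%.
- No blocking: 1/3, or 15 of 45.

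**Varying blocks.** These values come from simulation (6,000 runs per setting, sizes equally likely). The observer knows the menu of sizes and the full history of the stratum, and predicts optimally. The block-3 rows are exact.

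| Block sizes | Split | Certain, of 45 | Best guess | Excess over 1/3 |
|---|---|---|---|---|
| 3 | 22/23 | 14 | 59.6% | 0.263 |
| 3 | 21/24 | 15 | 61.1% | 0.278 |
| 3, 6 | 22/23 | 3.42 | 56.2% | 0.229 |
| 3, 6 | 21/24 | 3.66 | 57.2% | 0.239 |
| 3, 6, 9 | 22/23 | 1.39 | 53.8% | 0.205 |
| 3, 6, 9 | 21/24 | 1.42 | 54.4% | 0.211 |

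A larger but still fixed block does less for certain assignments: about 8.1 with block 6 and 5.3 with block 9, averaged over a 50:50 chance of either stratum.

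**Cost in balance, split 22/23.** The gap is the largest arm minus the smallest. The standard-error ratio is √[(1/a + 1/b)/(2/15)], where a and b are the two smallest arms.

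| Block sizes | Mean gap | 95th percentile gap | Maximum gap | SE increase, 95th percentile |
|---|---|---|---|---|
| 3 | 1.3 | 2 | 2 | 1.8% (15 v 14: √1.0357) |
| 3, 6 | 1.5 | 2 | 4 | 1.8% |
| 3, 6, 9 | 1.6 | 3 | 6 | 3.5% (14 v 14: √1.0714) |

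With sizes 3, 6 and 9 the worst case at this split is 18/15/12: √[(1/15 + 1/12)/(2/15)] = √1.125 = 1.061. At 21/24 a rare 19/13/13 is possible, if both strata stop three infants into a block of 9 with all three in the same arm: √(15/13) = 1.074.

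**The case against.** The strongest reply is that 14 or 15 is an upper bound for a fully informed observer. Deduction needs someone who influences enrolment, knows or infers the block size, and follows every earlier arm separately in each stratum. The protocol does not say who enrols. Its blinding statement covers only participants and the music therapist, who comes from a hired company. A control infant is recognisable only to someone who knows the infant is in the trial. Sample Selection and Sources of information also refer to units in the plural, and past arms would be harder to follow across several. All of this stands as a condition on the finding. It does not remove the concern, because the block size is printed in the protocol, gestational age is routinely recorded, and the arms are plainly different.

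Second, eligibility is largely objective, all eligible newborns are to enter, and heart rate comes from monitor records with a minute-0 value. That limits the harm and would show part of an imbalance at entry. It does not govern timing, and a baseline reading does not remove selection.

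Third, the remedy reduces overall predictability only modestly. Excess best-guess success falls by 13% to 14% with sizes 3 and 6, and by 22% to 24% with 3, 6 and 9. That is correct. The gain lies in the certain assignments.

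Fourth, small blocks give the tightest balance in a small trial, and nothing in the document contradicts a block of 3. True: this is a weak design choice, not an internal error, and the balance that would be given up is small.

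**Conclusion.** The concern holds. As written, 14 or 15 of the 45 assignments (31% or 33%) are fully determined by earlier ones, and a best guesser would be right for 59.6% to 61.1% overall. The first position in each block stays fully concealed. The count assumes that all 45 are enrolled, that the observer knows the block size, and that earlier arms in the stratum are known. The first and last are plausible for open arms in one NICU, and the second follows for anyone who has read the protocol.

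This establishes a route to selection bias, not that bias occurs, and the protocol gives no basis for an effect in bpm. It is a cheap improvement that should be made. It does not undermine the trial's validity by itself.

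**What to change.** In Sample Selection, replace the fixed size of 3 with randomly permuted blocks of randomly varying size within each gestational-age stratum. Sizes 3 and 6, or 3, 6 and 9, would serve. Record the sizes only in a document that enrolling staff do not see, and have the protocol say just that they vary and are withheld.

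The planned study period begins the day after the protocol date. If enrolment has started, leave used envelopes as they are, let each stratum finish its current block, and apply the new list from the next block boundary.

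The cost is one new Excel list and a replacement set of unused envelopes, plus the care needed when swapping lists in a two-month study. The price in balance is the small loss tabulated above. Sizes 3 and 6 give the tighter balance; adding 9 leaves fewer assignments certain. Sample size, arms, strata and analysis do not change.

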Gestational age at birth	Number of weeks gestation at the time of birth.	Quantitative – Continuous	Weeks and days of gestational age
Postnatal age at study entry	Age in hours or days since birth.	Quantitative – Discrete	Hours or days
Birth weight	Weight determined by a calibrated neonatal scale.	Quantitative – Continuous	Grams
Classification according to birth weight	Birth weight classification.	Qualitative – Nominal – Polytomic	1: Extreme low birth weight newborn (< 1000 grams) 2: Very low birth weight newborn (< 1500 grams) 3: Low birth weight newborn (< 2500 grams)
Birth Weight Percentile	Relationship between age, height, head circumference and weight.	Quantitative – Discrete	Percentile Value
Clustered Birth Weight Percentile	Comparison of the weight of the newborn with the rest of the same age and sex.	Quantitative – Discrete	1: Birth weight below the 10th percentile 2: Birth weight between the 10th and 90th percentile 3: Birth weight above the 90th percentile
Weight-for-gestational-age classification	Classification of weight in relation to gestational age at birth.	Qualitative – Ordinal – Polytomic	1: Small for gestational age 2: Suitable for gestational age 3: Great for Gestational Age
APGAR Score	A clinical visual examination performed on the newborn one minute and 5 minutes after birth to assess physiological adaptation to the extrauterine environment.	Quantitative – Discrete	Score from 0 to 10

APGAR Rating	Classification of neonatal adaptation to the extrauterine environment, given by the score in the APGAR criteria.	Qualitative – Nominal – Polytomic	1: Normal (7-10 points) 2: Moderate depression (4-6 points) 3: Severe depression (0-3 points)
Presence of comorbidities in the neonate	Presence or absence of associated diseases.	Qualitative – Nominal – Dichotomous	1: Yes 2: No
Name of the associated pathology	The medical term referring to the disease that the individual presents.	Qualitative – Nominal	Name of the disease
Perinatal history	Presence of important events during pregnancy.	Qualitative – Nominal	Background Name
Number of visits	Number of Parent Visits During the Day	Quantitative - discrete	Number
Singing	Emission of sounds or musical compositions by parents or legal guardian up to 30 minutes prior to the intervention.	Qualitative – Nominal – Dichotomous	1: Yes 2: No

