Sources of information

The source of information will be primary. Demographic and clinical data will be obtained from the medical record. The vital signs data such as heart rate, respiratory rate and oxygen saturation will be obtained from the records of the monitors of the intensive care units, at the established times, which are: at minute 0, from minute 0 to minute 10 continuously and at 30 minutes after the intervention.

Standardization of measurements

For the standardization of measurements of the different physiological variables, several elements will be considered. First, the trademark of the medical equipment manufacturer of each of the tools that will be used (vital sign monitor and pulse oximeter) will be verified, verifying that they correspond to the same commercial brand since they are different brands, there may be variability between the standard calibration measurements considered within the critical range. Second, it will be verified that each medical tool used has been calibrated in the last 6 months, recording the date of last calibration so that the device can be used during the study.

Subsequently, the professional in charge of the music company will verify that the guitar to be used during the live music is in tune and suitable for use. A decibel regulator will be used during the implementation of the pre-recorded and live music, which will adjust the volume of the sound emitted. to ensure the same decibels per research subject, with a maximum allowable of 70 dB. Vital variables will be recorded at minute 0, from minute 0 to minute 10 and at 30 minutes after the intervention.

Primary Outcome

The primary outcome of this study is the heart rate (HR), which will be measured through pulse oximetry every minute, beginning at minute 0 (prior to the intervention), then from minute 0 to minute 30 (during the intervention), and finally at 30 minutes after the intervention.

Secondary Outcomes

- Respiratory rate (RR) will be measured through pulse oximetry every minute, beginning at minute 0 (prior to the intervention), then from minute 0 to minute 30 (during the intervention), and finally at 30 minutes after the intervention.
- Oxygen saturation (SO) will be measured through pulse oximetry every minute, beginning at minute 0 (prior to the intervention), then from minute 0 to minute 30 (during the intervention), and finally at 30 minutes after the intervention.

Analysis of information

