A descriptive analysis of the variables will be performed using absolute and relative frequencies for the qualitative variables, as well as measures of central tendency and dispersion for the quantitative variables according to their normal distribution evaluated through the Kolmogorov-Smirnov test. To compare the data between the groups, one-way ANOVA or Kruskal-Wallis and chi-square ANOVA will be used. To determine the effect of music therapy on vital signs, repeated measures ANOVA or the Friedman test, if applicable, will be used. Assumptions of normality, homoscedasticity and residual distribution will be evaluated. Post-hoc comparisons are performed to determine significant differences between groups using the Student t-test. The level of significance for statistical tests will be $p < 0.05$.

A multivariate logistic regression will be performed to evaluate the effect of music therapy on respiratory rate, heart rate and pulse oximetry, considering confounding variables such as the number of visits, parental singing prior to the intervention, admission diagnosis, gestational age, comorbidities and gender.

Ethical Considerations

This research will adhere to the ethical guidelines developed by the CIOM and the WHO, as well as the stipulations of the Declaration of Helsinki for research involving human subjects. This will ensure the respect and protection of human rights, as well as the protection of the life, health, privacy, and dignity of the study subjects (24). Furthermore, this research is founded upon the tenets of bioethics, with the objective of promoting and ensuring justice, beneficence, non-maleficence, and patient autonomy, as outlined in the Belmont report from 1979 (25). Additionally, this research will have a social and scientific value, as its findings could potentially enhance the health of subjects and transform the manner in which care is delivered through the generation of reliable and valid results derived from a clinical trial. The researchers are highly qualified for the development of this research due to their expertise in pediatric and neonatal medicine, as well as epidemiology. For the administration of the interventions, a company with a high trajectory and experience in these interventions will be hired.

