In accordance with the provisions of Resolution 8430 of 1993 (26) of Colombia, as the population of this study is minors, who in this case are newborns who, due to their neurocognitive development, cannot exercise the principle of autonomy *per se*, this will be delegated to their guardian or legal representative through the completion of informed consent. The objectives and methodology of the research will be clearly explained to the legal representative of the neonate, including the type of music to be used, the daily duration of each session, the time of exposure, and the data to be collected. Conversely, the legally appointed representative will be permitted to observe the child's participation in the study as it progresses, provided that this does not result in any direct alteration of the results through manipulation or direct contact with the patient. This is to ensure that the principle of autonomy is not violated. Furthermore, the legal representative of the newborn will have the option to withdraw from the study at any time, without affecting the medical care of the newborn. This study is classified as a research study with a higher than minimum risk because the intervention can modify the physiological variables of the newborn. However, based on previous studies conducted nationally and internationally, it can be determined that the use of music therapy is at least as safe and advantageous, in light of the foreseeable risks and benefits, as any other established effective alternative.

In order to guarantee the privacy and confidentiality of the information of the subjects involved in the study, the provisions of the Habeas Data Law (Law 1581 of 2012) and Resolution 1995 of 1999 will be taken into account. An alphanumeric code will be used to identify the study subjects. Only the researchers will have access to the databases, and the data will be safeguarded for up to one year after the publication of the results. No sensitive information will be disclosed in the publication or in other

documents drafted during the investigation. The results of this research will only be used to provide new knowledge and encourage new studies.

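### The covariate for number of parent visits has no cut-off before allocation, so the adjusted regression may condition on visits that follow randomisation

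*Protocol*

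**What the plan says.** The Variable Matrix in the protocol defines the number of visits as "Number of Parent Visits During the Day", measured as a plain number. It does not say which day is meant, and it does not stop the count at allocation or at the start of the session.

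The next row, Singing, does carry a window. It records singing "by parents or legal guardian up to 30 minutes prior to the intervention".

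Analysis of information plans a regression that relates the intervention to the three vital signs. It describes the adjustment in that model as "considering confounding variables such as the number of visits, parental singing prior to the intervention" and goes on to list baseline factors. The same section names repeated-measures ANOVA or the Friedman test as the method for determining the effect on vital signs, and mentions no covariates there.

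Four other statements bear on timing and on whether the arm could influence visiting:

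- Primary Outcome: heart rate is read at minute 0, during the session, "and finally at 30 minutes after the intervention".
- Blinding: "It is not possible to blind the participants or the music therapist from randomization due to the nature of the intervention".
- Description of interventions: for Group A, guardians are involved in the choice of lullabies, "which will be selected by the patients' legal guardians".
- Ethical Considerations: the representative "will be permitted to observe the child's participation in the study as it progresses".

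**The concern.** A confounder in a randomised comparison has to be fixed before allocation. A count over the day is not, unless the session always comes after the last visit, and nothing in the protocol says so. The count can therefore mix three kinds of visit:

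- visits before allocation, which are a legitimate baseline covariate;
- visits between allocation and the last reading, which could at most lie on the path from arm to outcome;
- visits after the last reading, which cannot have influenced it.

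If the arm alters the second or third kind, and visiting is linked with the infant's vital signs, conditioning on the total breaks the balance that randomisation provided. The adjusted arm effect is then biased, although the unadjusted one is not.

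The matter also has to be settled before data are collected. If the form holds only a daily total, no later analysis plan can separate visits before the cut-off from those after it.

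**Working it through.** The protocol gives no figure for visits, so there is none of its own to reproduce on this point. The check has two parts.

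**1. Timing, from the text**

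| Item | Window in the protocol | Before allocation? |
|---|---|---|
| Singing | Up to 30 minutes before the session | Before the session by definition |
| Number of visits | The day, no cut-off | Not guaranteed |
| Last vital-sign reading | 30 minutes after the session | Later visits cannot affect it |

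No other section supplies a window for visits.

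**2. What adjustment could do, with assumed values**

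Let τ be the true arm effect, d the effect of the arm on the visit count, and β the slope of heart rate on visits within arms. In a linear model the adjusted arm effect is

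τ − d·β.

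The bias is −d·β. It is zero if the arm does not change visits (d = 0) or if visits are unrelated to heart rate (β = 0). Its sign depends on the signs of d and β.

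τ = 140 − 147 = −7 bpm, from the live and control means under Sample size. Every other input is an assumption.

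*Direction A: an unsettled infant has a higher heart rate and receives more visits.* HR = 147 − 7·arm + 6U + noise (SD 8). Visits = 2 + d·arm + g·U + noise (SD 0.9). Then β = 6g/(g² + 0.81).

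| d | g | β | Adjusted effect (bpm) |
|---|---|---|---|
| 0.5 | 0.3 | 1.8/0.90 = 2.00 | −7 − 1.00 = −8.0 |
| 0.5 | 0.5 | 3.0/1.06 = 2.83 | −7 − 1.42 = −8.4 |
| 1.0 | 0.3 | 2.00 | −7 − 2.00 = −9.0 |
| 1.0 | 0.5 | 2.83 | −7 − 2.83 = −9.8 |

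*Direction B: the factor that raises visits lowers heart rate.* Visits before the session are Poisson with mean 1.5 + 0.5U, and later visits are Poisson with mean 1.5 + d·arm + 0.5U, both means floored at 0.05. Heart rate moves by b bpm per SD of U, with total within-arm SD 15. The protocol states no SD. The value 15 is one at which the stated means and 45 infants give about 90% power (0.903) in a three-group ANOVA. Results from 400,000 simulated infants per scenario:

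| b | d | Whole-day count | Pre-session count |
|---|---|---|---|
| −3 | 0.5 | −6.58 | −7.00 |
| −3 | 2 | −5.82 | −7.10 |
| −6 | 1 | −5.62 | −6.87 |
| −9 | 0.5 | −5.98 | −7.07 |
| −9 | 2 | −3.41 | −7.00 |
| 0 | 2 | −6.97 | −6.95 |
| −9 | 0 | −7.01 | −7.01 |

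The formula agrees at both ends. Ignoring the floor, the pooled within-arm variance of the whole-day count is 4 + d/2 and its covariance with heart rate is b. For b = −3, d = 0.5: −7 + 0.5 × 3/4.25 = −6.6. For b = −9, d = 2: −7 + 2 × 9/5 = −3.4.

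The last two rows confirm that there is no bias when either condition is absent. The pre-session count stays within simulation error of −7 in every row.

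**The case against.** The strongest reply is that this is an underspecified definition and not a stated error. The protocol gives no clock time for sessions and does not say which day is counted. If sessions run late, most visits come before minute 0. A reader might infer that the greater part of the counted day lies after the last reading, and the documents do not support that. What stands is that inclusion of later visits is the plain reading and nothing excludes them.

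Second, a reader might take the right to observe as evidence that visiting differs by arm. It is not: Ethical Considerations gives that right without distinguishing arms. Choosing lullabies in Group A is also not a visit. Lack of blinding makes an arm effect on visits possible, no more.

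Third, the bpm figures carry little weight. All inputs on visiting are assumed, d = 1.0 in direction A is about one within-arm SD of visits, and the two directions move the estimate opposite ways. The illustration is linear, whereas the protocol names a logistic regression, so no bpm shift is an estimate from the planned model. With 15 per arm and the residual SD of 10 in direction A (√(36 + 64)), the standard error of a two-arm difference is 10 × √(2/15) ≈ 3.7 bpm, larger than the 1.0 to 2.8 bpm shift there. All of this stands and limits the claim to a possible bias of unknown size and sign.

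Fourth, the covariate list is illustrative, and exact windows may be set in an analysis plan that is not shown. That is fair for how the model is specified. It does not help if only a daily total is collected.

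**Conclusion.** The point holds in a limited form. As defined, the visit count is not confined to the period before allocation, yet it is to be adjusted for as a confounder. Visits after allocation cannot confound a randomised comparison, and adjusting for them can bias the adjusted arm effect in either direction. That needs both an effect of the arm on visiting and a shared cause of visits and vital signs. The protocol shows neither.

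The size cannot be fixed from the documents. The ranges of −9.8 to −8.0 and −6.6 to −3.4 bpm against a true −7 only show that the bias need not be trivial and that its sign is open.

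A reader might infer that the main comparison is threatened. It is not: the repeated-measures ANOVA or Friedman comparison does not use the visit count. Only the covariate-adjusted regression is exposed. The correction is still worth making, because it is small and may be impossible once only daily totals have been recorded.

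**What to change.** In the Variable Matrix, redefine the variable as the number of parent visits on the session day before allocation, at the latest before minute 0. This brings it into line with the pre-intervention window for Singing. Allocation is the cleaner cut-off, because asking Group A guardians to choose songs could itself prompt a visit between allocation and minute 0. In Analysis of information, state that only this count enters the regression and that later visits are not adjusted for.

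The cost is small but not nil. It takes one changed row, one clarifying sentence, and a data form that records the count at the cut-off. A daily total cannot be split afterwards, so the existing definition would not yield the needed count.
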